## **5 INVESTIGATIONAL PLAN**

### **5.1 Endpoints**

#### **5.1.1 Efficacy Endpoints**

This study is a preliminary, case/control study comparing food allergen elimination and food allergen elimination with PAN-5 for metabolic acceleration. The endpoint will be the 90-day completion of this trial

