The dependent variables in that study were changes in weight (pounds) and 'Body Summation' of 10 girth measurements (neck, shoulders, waist, hip, etc.). A 2x2 ANOVA was used to calculate differences. There was a significant difference between groups ( $P < 0.0001$ ), and the mean changes were as follows: Exp = -18.0lbs and -18.7" vs. Control +1.3lbs and +1.7." [16]

Eating natural, unprocessed foods was discussed in a portion size study [13] and Polsen et al examined differences from changing one's diet to natural foods in the New Nordic Diet [40]. They compared the 'Average' diet (control) to the New Nordic Diet (NND) which removed the processed foods and substituted with natural foods (high in fruits, vegetables, fish, and whole grains). In that study 181 obese subjects (mean age 42) were randomly selected to either the NND group or the Average diet for 26-weeks.

The dependent variable was change in weight and there was a significant difference for the NND vs Average group. The NND subjects showed a mean change of -4.7 kg vs the Average group lost only a mean -1.5kg ( $P < 0.001$ ). There were also significant differences seen in Fat change (1.87% difference,  $P < 0.001$ ), Waist circumference (-2.94cm difference,  $P < 0.001$ ), and in Systolic blood pressure (-5.13 mm Hg difference,  $P < 0.001$ ) [40].

These studies show the overlapping benefits from reducing Portion sizes (with greater meal frequency) and Aerobic-surge or brief, high intensity exercise, plus the benefits of eating Natural foods. The **purpose** of this study was to determine if removing food allergens alone or combined with a multi-discipline weight loss protocols are effective in obesity reduction.

This proposed study will have two volunteer, unrandomized groups: Food Allergen elimination (alone) vs. Combined Treatment (Food Allergen elimination + PAN-5). After 90-days the changes will be tested and compared.

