### **5.2 Study Design**

This is a pilot study comparing these two categories for weight loss.

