## **8. STUDY ASSESSMENTS**

### **8.1 Study Schedule of Events**

A screening phone call will evaluate the following:

- Eligibility (BMI, age, etc.)
- Medication eliminations (i.e. insulin, propranolol, etc.)

The initial meeting at the clinic will include the following:

- Informed consent and description of the study
- Confirmation of study eligibility
- Review of full medical history

Meeting for Enrolment will include the following:

- Consultation with PI
- Collection of blood through venipuncture for Food Allergen testing
- Demonstration of Aerobic-surge protocol and testing that subject understands
- Physical Examination
- Enrolment
- Initial Body Composition Testing.

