### **8.3 Efficacy Assessments**

Not applicable.

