## **11 STATISTICAL METHODS AND PLANNED ANALYSES**

### **11.1 General Considerations**

The dependent variables will include change in Body Composition (weight, Fat%), and BMI.

Independent variables will include age, gender, ethnicity, and duration of obesity.

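### The efficacy endpoint in 5.1.1 is completion of the trial rather than an outcome, 8.3 disclaims efficacy assessments, and no section schedules the day-90 measurement that the planned comparison needs

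*Protocol*

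**What the plan says.** The intended comparison is clear from the narrative sections of the protocol. The end of the Introduction describes two volunteer, unrandomised groups, food allergen elimination alone and elimination plus PAN-5, and says "After 90-days the changes will be tested and compared". Section 5.2 adds "This is a pilot study comparing these two categories for weight loss". The first sentence of 5.1.1 describes a study "comparing food allergen elimination and food allergen elimination with PAN-5 for metabolic acceleration".

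The sections that should put this into operation read as follows.

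- 5.1.1, Efficacy Endpoints, continues: "The endpoint will be the 90-day completion of this trial".
- 8.1, Study Schedule of Events, runs from the screening call to the enrolment meeting. Its last item is "Initial Body Composition Testing".
- 8.3, Efficacy Assessments, reads in full "Not applicable".
- 11.1 states "The dependent variables will include change in Body Composition (weight, Fat%), and BMI" and "Independent variables will include age, gender, ethnicity, and duration of obesity".
- The Synopsis names a repeated measures ANOVA for changes in weight, body composition and BMI.
- 11.3 defines the safety dataset by completion of 30-day assessments.
- 11.7 gives the method of body composition testing (electrical impedance) but no visit or day.

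**The concern.** An efficacy endpoint should be a variable measured on each subject at a stated time. Completing a 90-day trial is not a measure of obesity reduction, which is the stated purpose in section 4. With three candidate variables in 11.1 and none marked as the endpoint, the choice of which one carries the conclusion stays open until the data have been seen.

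The measurement gap is the more serious practical matter. Staff who work from 8.1 and 8.3 find no outcome test after enrolment and a statement that efficacy assessments do not apply. A day-90 weight or body composition reading that is not taken on the day cannot be recovered later, and without it neither a change nor a group difference in change can be calculated.

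**Working it through.** The protocol gives no effect size, standard deviation, power or dropout figure that bears on this point, so there is no figure of its own to reproduce. The check sets the sections side by side and counts.

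1. **Endpoint.** Outcome variables named in 5.1.1: 0. Candidate variables in 11.1: 3 (weight, Fat%, BMI). Variables marked as the endpoint or tied by name to day 90 in any section: 0. The 90-day time for the comparison comes from the Introduction; 5.2 states the comparison without a time.

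2. **Measurements.** A change score, or a repeated measures ANOVA over time, needs at least 2 measurements per subject. Section 8.1 lists 1 body composition test, at enrolment, and 0 after it. The shortfall is 2 − 1 = 1, and no other section supplies it: 8.3 disclaims efficacy assessments, 11.7 gives only a method, and 5.2.1 says subjects are followed for 90 days without naming a test.

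3. **Direct conflict or gap.** Section 8.3 cannot be true together with the Introduction's test of changes after 90 days, or with the change variables in 11.1 and the Synopsis. That is a contradiction. Section 8.1 is different: its list stops at enrolment and says nothing of later visits, so it is incomplete. The 30-day assessments in 11.3 fall in the same gap, since they define a dataset but are not scheduled.

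4. **Model terms.** Independent variables listed in 11.1: 4 (age, gender, ethnicity, duration of obesity). Of these, treatment group: 0. The sentence says what the variables will include, so the list need not be complete, and the Introduction, 5.1.1 and 5.2 already name the two groups to be compared.

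5. **Precision of the group contrast once it is specified.** For an unadjusted comparison of mean change, the 95% CI half-width in units of the SD of change is t(0.975, n1 + n2 − 2) × √(1/n1 + 1/n2). The Synopsis gives 18 patients and 11.2 gives 20. An equal split is assumed here, because the protocol lets subjects choose their group and fixes no ratio; full day-90 data and a common SD are also assumed.
   - 9 and 9: t(0.975, 16) = 2.120; √(2/9) = 0.471; half-width 1.00 SD.
   - 10 and 10: t(0.975, 18) = 2.101; √(2/10) = 0.447; half-width 0.94 SD.

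Step 5 describes what the corrected plan could deliver. It does not measure the defect, which rests on the counts in steps 1 to 4.

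**The case against.** The best defence is that a sensible reader can work out what is meant. Sections 5.2.1, 5.2.1.1 and 5.2.1.3 use completion to mark the 90-day point, so 5.1.1 may be loosely saying when the outcome is read. The outcomes are named in the Synopsis and 11.1. An initial test presupposes a later one. The study is a self-described pilot, and model terms normally belong in a statistical analysis plan.

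Much of this stands, and it rules out three stronger readings that a reader might infer.

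- *That no outcome will be measured after enrolment.* The Introduction and 11.1 require a later measurement; the fault is that it is not scheduled.
- *That a time-only ANOVA without group is planned.* Nothing says so. The two-group comparison appears in three places, and the analysis plan may well write out the group terms.
- *That 11.1 contradicts the group comparison.* It omits one term from an open list.

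The defence does not rescue the endpoint sentence, 8.3 or the schedule. Endpoint definitions and scheduled assessments are protocol content. An analysis plan cannot add a visit or undo a statement that efficacy assessments do not apply. Pilot status does not help either, since the protocol has an efficacy purpose and sets a 0.05 significance level in 11.8.5.

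**Conclusion.** The point holds and should be corrected before the study runs. Its size is textual: no outcome variable in the efficacy endpoint, three unranked candidates elsewhere, one of the two measurements needed, and a direct contradiction between 8.3 and the Introduction, 11.1 and the Synopsis. The absence of treatment group from 11.1 is a minor clarification.

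Error-rate calculations would not size this defect. A power figure for a time-only test would presuppose an analysis that the protocol does not plan. A bias figure for self-selected groups would describe a problem that remains after this correction. A multiplicity figure would depend on correlations that the protocol does not give. The conclusion needs none of these and no assumed values; it assumes only that the sections are read as they stand and that the missing analysis plan cannot amend the visit schedule.

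**What to change.** 1. **5.1.1.** Name one variable already in 11.1 (for example body weight), as change from enrolment to day 90, as the primary endpoint. Make the others secondary.
2. **8.1 and 8.3.** Replace the present entry in 8.3, and list the day-90 weight and body composition test in 8.1. Either schedule the 30-day assessments or remove the reference to them in 11.3.
3. **Design labels and 11.1.** Reconcile the three descriptions of the design: randomised cross-over (Synopsis and Summary of Potential Risks), case/control (5.1.1 and 5.3), and volunteer groups without randomisation (end of the Introduction, 7.2 and 7.3). If the volunteer groups are kept, add treatment group to 11.1 as a clarification, report the between-group difference in change with its 95% CI, and call it a non-randomised exploratory comparison. The role of the four patient characteristics can be left to the analysis plan.

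The cost is an amendment of wording plus one listed assessment that the Introduction already implies. Only one outcome would then carry the primary claim, and the protocol would have to be open that the group contrast is imprecise: a half-width of 0.94 to 1.00 SD of change at an equal split, and wider if the volunteers divide unequally.

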#### **5.1.2 Safety Endpoints**

Only serious adverse events (SAEs) associated with study procedures will be recorded.

#### **5.1.3 Other Endpoints**

N/A

### **5.2 Study Design**

This is a pilot study comparing these two categories for weight loss.

#### **5.2.1 Completion of a Subject's Participation and the Overall Study Completion**

Each subject's will be followed through completion of the 90-day trial.

##### **5.2.1.1 Completion of a Patient's Participation in the Study**

Participation in the study will be completed after 3 months. Each patient will have daily communication (text) with the clinical staff in the first 30 days, and weekly communication through the first 3 months.

##### **5.2.1.2 Premature Patient Discontinuation from the Study**

Patients are free to withdraw consent and/or discontinue participation in the study at any time, without prejudice to further treatment. A patient's participation in the study may also be discontinued at any time at the discretion of the Principle Investigator or Primary Care Physician.

##### **5.2.1.3 Overall Study Completion**

The study will be considered to be complete after 90-days.

### **5.3 Discussion of Study Design**

This is an Investigator-Initiated, preliminary case/control study. A

## **6. SUBJECT Population and Selection**

### **6.1 Inclusion Criteria**

A subject must meet all of the following criteria to be eligible for this study.

1. The subject is > 20 years of age and is willing and able to provide signed informed consent.
2. The subject has a BMI > 30.
3. The subject is between the ages of 20 to 75 years of age.

### **6.2 Exclusion Criteria**

A patient who meets any of the following criteria will be excluded from this study.

- 1) Cardiovascular Heart Disease and this includes but is not limited to history of myocardial infarction, atrial fibrillation, etc.
- 2) History of cerebral vascular event (stroke), traumatic brain injury, Parkinson's disease or any other neural injury or disease.
- 3) Diabetes Mellitus (Type I or II)
- 4) Pregnancy
- 5) Participation in any other weight loss protocols, diets, or medication.

## TREATMENTS

The treatments will include the following:

- Elimination of foods showing any leukocyte reaction (tests all Ig reactions).
- Restructure of dietary schedule of eating to < 2 cups of food, five times each day.
- Participation in the 2-minute Aerobic-surge exercises (with HR  $\geq$  75% max HR) performed at home or work, five times per day.
- Consuming Natural foods five times a day, (included in the total 2 cup volume), 5/day.

### 7.1 Prior and Concomitant Medications and Therapeutic Procedures

Concomitant medications and therapies the patient has taken in the week prior to enrollment will be recorded during the first study visit. Patients will be excluded from enrollment in the study if they have taken or are currently taking medication for weight loss such as Phentermine, medication for insulin control, or medication for HR (propranolol).

### 7.2 Method of Assigning Patients to Treatment

All subjects will receive food allergen testing and they can volunteer to also be treated with the PAN-5 protocol.

### 7.3 Blinding and Randomization

- No blinding or randomization will occur.

### 7.4 Treatment Compliance

Compliance will be tracked through daily communication with staff (daily text messages or paper recordings of daily compliance to be turned in weekly) and this will be done through the 90-day duration of this trial.

## **8. STUDY ASSESSMENTS**

### **8.1 Study Schedule of Events**

A screening phone call will evaluate the following:

- Eligibility (BMI, age, etc.)
- Medication eliminations (i.e. insulin, propranolol, etc.)

The initial meeting at the clinic will include the following:

- Informed consent and description of the study
- Confirmation of study eligibility
- Review of full medical history

Meeting for Enrolment will include the following:

- Consultation with PI
- Collection of blood through venipuncture for Food Allergen testing
- Demonstration of Aerobic-surge protocol and testing that subject understands
- Physical Examination
- Enrolment
- Initial Body Composition Testing.

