“PAN-5” is an effective combination of separately proven protocols and the acronym includes the following: **P**ortion sized meals (<2 cups, 5/d) [12-14], **A**erobic-surge Exercise for 2-minyes, 5/d) [15-39], and **N**atural foods which must be eaten 5 times/day [40-44]. A portion-sized study with adult subjects was completed by Kesman et al who examined 65 obese adults (Mean age 55.8 and BMI > 30 to 40) and their intervention included a Portion-size plate (2 cups) with separations for food groups. After six months there was a significant change between experimental vs control groups (P=0.41) and the mean changes were -2.4% Δ body weight for Portion Plate vs +2.2% Δ body weight for the control group [12].

A landmark study examining the frequency of eating and portion size was done by Iwao et al. on Olympic boxing athlete's weight loss in a two week study. Twelve boxers were separated into two categories, one group ate 6 meals/day (6M) and one group ate 2 meals/day (2M). The exact same daily food quantities were divided into 6 meals or two meals, and all boxers had similar exercise and training regime [14].

Both groups lost weight and while there was not significant difference in the weight change, the 6M group had a 90% greater change in body fat than the 2M group. This study showed that eating smaller portions sizes, more frequently, yielded greater fat reduction in the 6M group [14].

High intensity exercises with brief durations have been a recent addition to the protocols used in weight loss. A study by Fisher et al, titled "High Intensity Interval - vs Moderate Intensity - Training for Improving Cardiometabolic Health in Overweight or Obese Males: A Randomized Controlled Trial" showed resounding evidence supporting this protocol. High Intensity Interval Training (HIIT) vs a common moderate intensity training (MIT) for weight loss were tested in twenty-eight healthy, overweight or obese males, (age 20, BMI 25 - 35) and this study lasted 6 weeks [15].

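### Section 8.1 does not limit the Aerobic-surge training to subjects who choose PAN-5, so the elimination-alone group faces a contamination risk that the protocol neither prevents nor records

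*Protocol*

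**What the plan says.** **Groups.** Protocol section 3.1 (Introduction) sets up the comparison: "This proposed study will have two volunteer, unrandomized groups: Food Allergen elimination (alone) vs. Combined Treatment (Food Allergen elimination + PAN-5". The same section makes Aerobic-surge exercise the second element of PAN-5, beside portion size and natural foods. Section 5.1.1 repeats the two-group comparison.

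**Assignment.** Section 7.2 makes testing universal and PAN-5 optional: "All subjects will receive food allergen testing and they can volunteer to also be treated with the PAN-5 protocol". It does not say when the choice is made. Section 7.3 rules out blinding and randomization.

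**Enrolment meeting.** Section 8.1 gives one list, opened by "Meeting for Enrolment will include the following", and that list contains "Demonstration of Aerobic-surge protocol and testing that subject understands". The item follows the blood draw, precedes the physical examination, and comes before the item for enrolment itself. No group is named.

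**Treatments.** Section 7 lists four components together: elimination, the meal schedule, the exercise ("Participation in the 2-minute Aerobic-surge exercises (with HR" at or above the stated threshold), and natural foods. It does not say which group receives which.

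**Compliance.** Section 7.4 tracks compliance by text message or paper record. It does not say that exercise by elimination-alone subjects is captured.

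**The concern.** PAN-5 is the only planned difference between the groups, so what the elimination-alone group is taught about PAN-5 matters. A site following section 8.1 to the letter would demonstrate the exercise to subjects who had not chosen it and check that they understood it. They would be people seeking to lose weight, unblinded, and able to do the exercise at home or at work.

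Section 4 asks whether elimination works alone and whether it works in combination. If some elimination-alone subjects exercise, and the exercise reduces weight as the protocol expects, both answers are affected. The elimination-alone change is overstated, because weight lost through exercise is credited to allergen removal. The difference between groups is understated. Without a record of uptake, neither effect could be seen or allowed for afterwards.

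**Working it through.** The protocol attaches no figure to this point, so there is nothing to reproduce. The check is a reading of the text followed by an illustration.

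**Step 1: is the training limited to one group anywhere?**
- Section 8.1: one list, no group named. The neighbouring items (blood draw, physical examination) apply to all subjects.
- Section 7: one list, no group named.
- Synopsis (Safety) and section 9.1: the exercise is treated as a general study procedure.
- Summary of Potential Risks: exercise injury is given as a study risk, again with no group named.
- Sections 3.1 (Introduction), 5.1.1 and 7.2: these separate the groups, but none says that training is withheld from elimination-alone subjects.

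The literal reading of 8.1 therefore reaches both groups. A reading confined to PAN-5 volunteers is possible only by carrying 7.2 into 8.1.

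**Step 2: does teaching matter by the protocol's own evidence?** In the Aerobic-surge trial described in the Introduction, the experimental subjects were taught to reach the target heart rate, and the controls were only told to exercise more. Section 8.1 read literally gives this trial's comparison group the teaching that those controls did not get.

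**Step 3: size, for illustration.** Inputs from section 3.1 (Introduction): mean change −18.0 lb with Aerobic-surge and +1.3 lb in controls over 60 days; −5 kg over 90 days in the cited elimination study. The Synopsis gives 18 patients and section 11.2 gives 20. Assumptions: equal groups, the full cited effect in each subject who takes up the exercise, and effects that add.

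- Cited difference: 18.0 + 1.3 = 19.3 lb; 19.3 × 0.4536 = 8.75 kg.
- Shift in the elimination-alone mean when k of n subjects take it up: (k / n) × 8.75 kg.
- 18 patients, n = 9, k = 1: 8.75 / 9 = 0.97 kg, which is 0.97 / 5 = 19% of the cited elimination change.
- 20 patients, n = 10, k = 1: 8.75 / 10 = 0.88 kg.
- k = 0: no shift.

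The contrast falls by the same amount. With one of nine taking it up, the exercise part of the contrast keeps 1 − 1/9 = 89% of its value. Because subjects choose their group, n may not be 9 or 10; a smaller elimination-alone group would make one subject count for more.

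**The case against.** **The list may not mean everyone.** Section 8.1 is a brief outline, and 7.2 says PAN-5 is for volunteers. A sensible site might demonstrate the exercise only to them. This stands as far as it goes: the protocol does not say outright that every subject is trained, and that is an inference from an unrestricted list. But if the text allows two readings of who receives an intervention component, it should be settled.

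**Being shown an exercise is not doing it.** This stands. A reader might infer that the elimination-alone group is contaminated. The documents do not support that: nobody tells these subjects to exercise, and no uptake figure is given. Those who wanted the exercise could have chosen PAN-5, which may make uptake among the rest low.

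**Section 7 does not give everything to everyone.** A reader might infer from the undivided list that all subjects receive all four components. That would contradict sections 3.1 (Introduction), 5.1.1 and 7.2. The list is better read as an inventory that has not been divided by group.

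**The illustration is at the upper end.** It gives a subject who saw a demonstration the full effect found in subjects assigned to the regimen, and sets a 60-day result beside a 90-day result from a different, overweight population. This stands: it shows how sensitive a small group mean is, not the likely bias.

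**The cross-over label.** The Synopsis and the Summary of Potential Risks call the trial a randomized cross-over, under which training everyone would be less odd. Sections 3.1 (Introduction), 7.2 and 7.3 contradict that label, and training before an elimination-alone first period would still expose that period.

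**Restricting the demonstration does not remove knowledge of the exercise.** True, since the study is described to everyone at consent. That is why recording use in both groups is part of the fix.

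**Conclusion.** The point holds as a contamination risk created by unrestricted wording in section 8.1 and an undivided treatment list in section 7, with no provision in 7.4 to detect it. The direction follows if the exercise has any effect on weight: the elimination-alone change is inflated and the group contrast is reduced. The magnitude is unknown. About 1 kg per fully responding subject in an assumed group of 9 is an illustration resting on the assumptions above, and with no uptake the bias is zero.

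Severity is moderate. In an unblinded, unrandomized pilot of 18 or 20, self-selection into groups threatens the same contrast more seriously. The two problems are separate, and correcting this one leaves self-selection in place.

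**What to change.** 1. **Section 8.1:** record the subject's group choice first, then limit the demonstration and comprehension check to subjects who chose PAN-5.
2. **Section 7:** reconcile the list with sections 3.1 (Introduction) and 7.2 by stating which listed components belong to which group.
3. **Section 7.4:** ask both groups, in the existing texts or paper records, whether they used any PAN-5 component. The frequency of these contacts differs between sections 5.2.1.1, 7.4 and 11.6; the question can go with whichever schedule is kept.
4. **Reporting:** give the share of elimination-alone subjects who used a PAN-5 component beside the group results.

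The cost is protocol wording, one more compliance question and slightly more reporting. No extra visits or subjects are needed. The change has to be made before enrolment, because training already given cannot be withdrawn.
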